### 8.2 CLINICAL LABORATORY TESTS

Blood and urine samples will be obtained for assessment of clinical laboratory parameters. Clinical laboratory assessments (haematology, chemistry, urinalysis) will be performed on the visits as described in the schedule of study assessments and procedures in the protocol.

Clinical laboratory parameters at all scheduled visits will be summarised using appropriate descriptive summary statistics.

Period-specific baseline values will be used (see Section 5.2.2). The change from baseline in each haematology and chemistry to each post-baseline visit will also be summarised by treatment group.

Shifts from baseline for laboratory results categories (Low, within normal range, high) to each study visit will be presented by treatment group for each laboratory parameter.

All clinical laboratory results will also be listed. Laboratory values that are outside the normal range will be flagged in the participant data listing. Listings of abnormal laboratory parameters will also be provided.

### 8.3 VITAL SIGNS

Vital signs data recorded in the study include systolic and diastolic blood pressure, pulse rate, temperature and arterial oxygen saturation (SpO2). Descriptive statistics of vital signs will be presented by treatment group for all scheduled visits using appropriate descriptive summary statistics.

Period-specific baseline values will be used (see Section 5.2.2). The change from baseline to each post-baseline visit will also be summarised by treatment group.

Clinically significant abnormalities will be summarised using count and percentages for vital signs overall interpretation at all scheduled visits by treatment group and cohorts.

All vital signs data will be included in subject data listings, and clinically significant abnormalities will be flagged.

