7.2 Inclusion criteria

- 1. Male and female subjects ≥40 years of age
- 2. Able to understand and comply with the requirements of the study and give informed consent
- 3. Diagnosis of IPF established according to the 2018 or 2022 joint ATS/ERS/JRS/ALAT Clinical Practice Guideline
- 4. FEV1/FVC ratio \geq 0.65 at the screening visit
- 5. Haemoglobin-corrected diffusion capacity of carbon monoxide ≥25% within 12 months of the screening visit⁵
- 6. Arterial oxygen saturation on room air or oxygen ≥90% at Screening
- 7. Life expectancy of at least 12 months
- 8. Cough that is attributed to IPF, which has not responded to anti-tussive treatment, and which has been present for at least 8 weeks prior to Screening
- 9. Mean daily IPF Coughing Severity Scale score ≥5 (after rounding) during the second week of the baseline assessment period (assessed at Visit 2)
- 10. If taking pirfenidone or nintedanib⁶, it must have been started at least 3 months prior to screening and the prescribed dose must have been stable for at least 1 month prior to screening
- 11. Female subjects must not be of child-bearing potential (i.e., they must be surgically sterilised or post-menopausal⁷)
- 12. Male subjects who have partners of child-bearing potential must agree to use a condom from the Baseline visit until 30 days after the last dose of study medication

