 - b. Strong or moderate inducers of CYP3A4 are not allowed from Screening until 1 week after the last dose of study medication
 - c. Strong or moderate P-glycoprotein inhibitors are not allowed from Screening until 1 week after the last dose of study medication
 - d. Angiotensin converting enzyme (ACE) inhibitors are not allowed within 3 months of Screening and throughout the study.
 - e. Other treatments for cough management (opioids, dextromethorphan, gabapentin, pregabalin, baclofen, antihistamines, thalidomide, benzonatate or tricyclic antidepressants (e.g. amitriptyline)) are not allowed from 4 weeks before the Baseline visit until Visit 8. Medications in these classes may be continued provided they have been prescribed solely for the management of another comorbidity and the dose has been stable for at least 4 weeks before the screening visit.
 - f. The use of other NK₁ antagonists (e.g., aprepitant, fosaprepitant, rolapitant) is not permitted for any reason from 4 weeks before the Baseline visit until completion of Visit 8
 - g. Immune-suppressant drugs and systemic corticosteroids taken for co-morbidities are permitted provided the dose has been stable for at least 2 weeks before the screening visit and they are expected to be used at this dose throughout the study. Any other use is prohibited.
 - h. Supplemental oxygen is permitted provided it has been used for at least 2 weeks before the screening visit and is expected to be used throughout the study.

Final V4.0 (US) Protocol No.: ORV-PF-01

⁸ The investigator should judge the clinical relevance of any abnormal laboratory parameters in the context of the subject's current and past medical history, and any know contributing factors

- 13. Participation in any clinical research study evaluating another investigational drug or therapy within 30 days or within 5 half-lives (whichever is longer) of the investigational drug prior to Screening. If the subject was in an observational clinical study, no washout is required
- 14. Subjects who have previously received orvepitant at any time
- 15. Known allergy to any of the excipients used in the investigational medicinal product (IMP) (orvepitant or placebo tablets)
- 16. Subjects who, in the opinion of the Investigator, should not participate in the study for any other reason.
- 17. Subjects who are dependent on the Sponsor, CRO or investigator for employment of education.

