9.8 Permitted Concomitant Medications

All concomitant medications taken during the study will be recorded in the eCRF with indication, dose information, and dates of administration. Any medication that is not specifically prohibited is allowed.

Throat or cough lozenges (also known as a candies, drops, sweets or pastilles) and mucolytic agents are permitted.

9.9 **Prohibited Concomitant Medications**

A list of prohibited concomitant medications is provided in Appendix 1.

Due to their potential effect on cough reflex sensitivity, the use of opioids, dextromethorphan, gabapentin, pregabalin, baclofen, antihistamines, thalidomide, benzonatate or tricyclic antidepressants (e.g. amitriptyline) for treatment of cough is not allowed throughout the study (through to Visit 8). Subjects must have discontinued these drugs at least 4 weeks prior to the Baseline visit and should not have them started during the study. Subjects may, however, be permitted to continue to use these drugs if they have been prescribed solely for the management of another disorder (eg neuropathic pain, depression) and the dose has been stable for at least 1 month prior to screening.

Protocol No.: ORV-PF-01 Final V4.0 (US) Page 41 of 85

Angiotensin converting enzyme (ACE) inhibitors are not allowed within 3 months of Screening and throughout the study.

The use of other NK_1 antagonists (e.g., aprepitant, fosaprepitant, rolapitant) is not permitted for any reason from 4 weeks before the Baseline visit until completion of Visit 8

Strong or moderate inhibitors of CYP3A4 are excluded from the day of Visit 2 until one week after the last dose of IMP in the study.

The following classes of medication are excluded from Screening until one week after the last dose of IMP in the study:

- Strong or moderate inducers of CYP3A4 (including but not limited to rifampicin, carbamazepine, efavirenz, bosentan, modafinil, St. John's Wort)
- Strong or moderate inhibitors of P-glycoprotein inhibitors

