10.2.8 Vital signs

Vital signs (systolic and diastolic blood pressure, pulse rate, temperature, arterial oxygen saturation [SpO2]) will be measured at Visits 1, 2, 4, 5, 7 and 8.

Blood pressure will be measured using a standardised process:

- Subject should sit for ≥5 minutes with feet flat on the floor and measurement arm supported so that the midpoint of the manometer cuff is at heart level
- Use an automatic blood pressure device with an appropriately sized cuff with the bladder centered over the brachial artery
- Measure and record the blood pressure using the same arm throughout the study

SpO2 will be measured using a pulse oximeter.

Additionally, weight will be measured at Visits 2 and 8.

All measurements are to be recorded on the Vital Signs eCRF.

All vital signs must be reviewed by the Investigator or delegated physician. The Investigator will comment on all abnormal results and determine whether they are clinically significant. These assessments will be recorded in the eCRF, and clinically significant findings must also be reported as adverse events in the eCRF.

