### **5.2.2** Baseline Values

Baseline values will be defined separately for each treatment period, unless stated otherwise.

For the primary efficacy endpoint (mean change from baseline to Week 4 in weekly average of the daily IPF Coughing Severity Scale score), period-specific baseline will be used in the analysis, which is the average of the 7 calendar days up to and including the date of Visit 2 for Treatment Period A and the average of 7 calendar days up to and including the date Visit 5 for Treatment Period B.

For secondary efficacy endpoints related to change from baseline, the period-specific baseline will be used when available; for those endpoints for which a period-specific baseline is not available

(cough frequency and Hull Airway Reflux Questionnaire), the baseline in Treatment Period A will be used.

For safety assessments, baseline will be Visit 2 for Treatment Period A and for Treatment Period B it will be Visit 5.

For both safety and efficacy assessments, if the period-specific baseline is missing for Treatment Period A the value from Visit 1 will be used. If this is missing change from baseline will not be calculated. If the period-specific baseline is missing for Treatment Period B the value from Visit 2 (first preference) or visit 1 (second preference) will be used. If both are missing change from baseline will not be calculated.

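### SpO2 change from baseline is summarised without regard to supplemental oxygen, so this one descriptive safety table can be biased towards no harm

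*SAP*

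**What the plan says.** **Analysis.** SAP 8.3 defines the variables: "Vital signs data recorded in the study include systolic and diastolic blood pressure, pulse rate, temperature and arterial oxygen saturation (SpO2". They are described by treatment group at each scheduled visit, and "The change from baseline to each post-baseline visit will also be summarised by treatment group". The baseline is period-specific: "For safety assessments, baseline will be Visit 2 for Treatment Period A and for Treatment Period B it will be Visit 5". SAP 8.3 also plans a count of abnormalities: "Clinically significant abnormalities will be summarised using count and percentages for vital signs overall interpretation at all scheduled visits by treatment group and cohorts". SAP section 8 rules out formal tests on safety data.

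**Measurement.** Protocol 10.2.8 standardises blood pressure (rest, posture, cuff, arm). For saturation it says only "SpO2 will be measured using a pulse oximeter".

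**Oxygen at entry and on study.** Inclusion criterion 6 reads "Arterial oxygen saturation on room air or oxygen ≥90% at Screening". Exclusion criterion 12h begins "Supplemental oxygen is permitted provided it has been used for at least 2 weeks before the screening visit" and adds an expectation that use will continue. Protocol 9.8 allows anything not expressly prohibited and states that "All concomitant medications taken during the study will be recorded in the eCRF with indication, dose information, and dates of administration". Neither Protocol 9.9 nor Appendix 1 lists oxygen.

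**Place in the trial.** Mean change in SpO2 is a named safety endpoint (Protocol 8.3, SAP 3.4), and safety is one of the two primary objectives (Protocol 6.1).

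**The concern.** A saturation reading is interpretable only alongside the oxygen in use when it was taken. Oxygen is given to hold saturation up. If a subject deteriorates between the period baseline and Week 4 and receives more oxygen, the two readings may be almost equal although the subject is worse. The raw change then records no harm in that subject. The error is not random: extra oxygen given for worsening moves the reported change towards zero.

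The trial enrols patients with a progressive lung disease and names respiratory decline as an AESI. If deterioration were more frequent under one treatment, the SpO2 columns could look alike and be read as reassuring. At stake is the reading of one descriptive table under the safety objective.

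**Working it through.** The documents state no figure for SpO2 change, its spread, or the share of subjects on oxygen, so there is no figure of the plan's to reproduce. The check is a comparison of provisions, followed by an illustration on assumed values.

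**Step 1. Is oxygen use fixed within a period?** Compare two neighbouring items in Protocol 7.3:
- 12g (immune-suppressants, systemic corticosteroids): stable before screening, expected to continue at the same dose throughout, any other use prohibited.
- 12h (oxygen): in use for 2 weeks before screening and expected to continue. There is no wording on a constant dose and no closing prohibition.

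Read with Protocol 9.8, an increase in an existing user is not restricted by 12h. Oxygen newly started on study is less clearly covered, because 12h speaks only of oxygen already in use. Whether or not a new start counts as a deviation, the SpO2 reading enters the summary in the same way.

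**Step 2. Is the reading tied to the oxygen in use?** Not in Protocol 10.2.8, and no other section of either document does so. Neither document says that readings are taken on room air or at the baseline flow, or that flow is noted beside the reading.

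**Step 3. Does the analysis compensate?** SAP 8.3 has no adjustment, split or flag for oxygen. The abnormality count uses the overall vital-signs interpretation, not SpO2 itself, and a reading restored by oxygen may not be called abnormal. The concomitant medication table in SAP 6.4 counts each drug once per subject by dose group, so an increase in an existing user does not show there, although all medications are listed.

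**Step 4. Illustration.** Inputs:
- n = 44 per cohort, from 88 subjects in two equal cohorts (Protocol 7.1), taking all as measured
- d = 4 points, a fall fully corrected by extra oxygen (assumed)
- m = number of such subjects in a treatment column (assumed)
- SD of change = 2 points (assumed)

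Shift in the column mean = d × m / n:

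| m | 4m/44 (points too favourable) | m/44 |
|---|---|---|
| 2 | 0.18 | 4.5% |
| 4 | 0.36 | 9.1% |
| 6 | 0.55 | 13.6% |

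Standard error of the column mean = 2/√44 = 0.30.

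A second case uses the 37 evaluable subjects per cohort. If 5 had a true fall of 2, 4 or 6 points, the mean change would be −5×2/37 = −0.27, −5×4/37 = −0.54 or −5×6/37 = −0.81. If extra oxygen restored all five, and nobody else changed, the table would show 0.00 each time.

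**Step 5. Between treatments.** The gap between the two columns of a cohort shifts by d × (m under orvepitant − m under placebo)/n. With 4 and 0 subjects it is 0.36; with 4 and 2 it is 4×2/44 = 0.18; with equal numbers it is zero. The comparison is distorted only if escalation differs between treatments, but each column is too favourable on its own whenever m is above zero.

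**The case against.** The strongest reply is that SpO2 is one descriptive line among several, and that the others do not depend on it.

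- Non-serious respiratory decline is an AESI (Protocol 10.5.1), and treatment-emergent AESIs are tabulated and listed (SAP 8.1). Serious events are reported as SAEs.
- Spirometry is summarised by treatment, at the same visits as SpO2 (SAP 8.6). Daily dyspnoea and K-BILD Breathlessness are analysed.
- The investigator reviews all vital signs, and clinically significant changes become adverse events (Protocol 10.2.8). SAP 8.3 also counts clinically significant abnormalities, so it is wrong to say that it reports only raw values and changes.

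All of this stands. A reader might infer that respiratory decline would go unreported; the documents do not support that. They leave a weakness in one table, which may appear to contradict the other routes.

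A reader might also infer that mixing room-air and oxygen users biases the comparison. It does not in itself: apart from dropouts, the same subjects contribute to both columns of a cohort, each against a period-specific baseline. Only a change of oxygen within a period matters.

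Third, no provision expressly permits flow changes. That they are unrestricted is inferred from the contrast between 12g and 12h, together with Protocol 9.8. The inference is fair, but the number of subjects affected is unknown.

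Finally, the assumed shifts are small: below one standard error at m = 2, just above it at m = 4, and under two at m = 6. No test or decision rule uses mean SpO2. This supports treating the point as minor. It also shows why a count of affected subjects would be more informative than the mean.

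**Conclusion.** The point holds as a limited one. Followed exactly as written, SAP 8.3 can report a change near zero for a subject who worsened and received more oxygen, and its abnormality count may miss the same subject. The bias, where it occurs, is towards no harm.

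Its size cannot be determined. It depends on how many subjects use oxygen, how many have it started or increased within a period, and how fully this restores the reading; the documents give none of these. The 0.18 to 0.55 points shown rest wholly on assumed values and indicate scale only. It would be too strong to say that a decline will be reported as no change, because that requires both an increase in oxygen and near-complete correction.

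The consequence is confined to a descriptive safety summary. The severity is minor; the reason to act is that the repair is cheap.

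**What to change.** This is a change to reporting only. No rule on the use of oxygen is proposed.

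1. Confirm that oxygen, with dose and dates, is recorded under concomitant medication. Protocol 9.8 requires these details for all concomitant medications but does not name oxygen, and the eCRF is not among the documents.
2. In SAP 8.3, use those records to flag each SpO2 change where oxygen was started or increased since the period baseline.
3. Report by treatment, within cohort: the number of subjects flagged; the SpO2 change in subjects with unchanged oxygen use; and a combined count of subjects with an SpO2 fall of a prespecified size, or oxygen started or increased. The sponsor should fix that size before unblinding.
4. Where enrolment is still open, record oxygen use and flow with each SpO2 reading. Dates and dose alone may not show what was in use when the oximeter was read.

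The cost is a paragraph in the SAP, one extra table and, if still possible, an addition to the vital signs eCRF page. The downside is fewer pairs in the unchanged-use mean. That mean also leaves out the subjects who needed more oxygen, so it should never be shown without the combined count. With 37 to 44 subjects per cohort, cells may be small; a further split by room air or oxygen should be made only if numbers allow.

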### 8.4 ECG DATA

ECGs will be assessed by the investigator for overall abnormal findings and will be classified as Normal, Abnormal not clinically significant or Abnormal clinically significant. These will be summarised by the proportion of subjects within each category at each post-baseline assessment by treatment group. Shift tables will also be presented.

The actual value and change from period-specific baseline (see Section 5.2.2) will be summarised descriptively by treatment group and time point for each ECG interval parameters by treatment group.

- **ECG** intervals:
  - ORS duration

- PR
- QT, QTc and QTcF
- RR

QTcF interval will be derived using: QT interval/(RR interval)^1/3

In addition, the proportion of subjects at each post baseline assessment with maximum absolute QTcF values by the following categories will be presented:

- <450 msec
- >450 to <480 msec
- >480 to <500 msec
- >500 msec

Similarly, the proportion of subjects at each post baseline assessment with increase from baseline in QTcF values by the following categories will be presented:

- <0 msec
- >0 to <30 msec
- >30 to <60 msec
- >60 msec

All ECG parameters will be listed.

#### 8.5 PHYSICAL EXAMINATION

Physical examination data include measurements as collected in the CRF such as General appearance, Skin, Head, eyes, ears, nose and throat, Respiratory, Cardiovascular, Abdomen (including liver and kidneys), Musculoskeletal, and Neurological.

A by-subject listing with physical examination findings will be provided.

#### 8.6 PULMONARY FUNCTION TESTS

Pulmonary function test (PFT) data recorded in the study include forced vital capacity, forced expired volume in 1 second and peak expiratory flow rate and vital capacity (VC). Descriptive statistics of the PFTs will be presented by treatment group for all scheduled visits and will be summarised using appropriate descriptive summary statistics by treatment group.

Period-specific baseline values will be used (see Section 5.2.2). The change from baseline to each post-baseline visit will also be summarised by treatment group.

Clinically significant abnormalities will be summarised using count and percentages for each parameter examined at all scheduled visits by treatment group.

All PFT data will be included in subject data listings.

## 8.7 TREATMENT COMPLIANCE AND EXPOSURE

Definitions of exposure variables are provided in Table 2.

Table 2: Exposure variables definitions

Variables	Definitions
Duration of dosing (days)	Last dose of treatment – first dose of randomised treatment +1  The first and last days of treatment in each treatment period is used to derive the duration of dosing for each treatment (placebo and orvepitant).
Study treatment compliance (%)	100 * (total number of doses taken) / (total number of doses planned to be taken)  Total number of doses taken is calculated using the eCRF pages 'Drug Accountability" and "Drug Dispensing", based
	on the following:  Each bottle contains 34 tablets which is sufficient for the full 28 day dosing period plus overage. Number of doses taken = number of tablets dispensed (at Visit 2 [Period A] or Visit 5 [Period B]) – number of tablets remaining in the bottle (at Visit 4 [Period A] or Visit 7 [Period B]).
	The total number of doses planned to be taken is the number of days between the first visit in the period (Visit 2 or 5) and the Week 4 visit (Visit 4 or 7) for each period. If a subject is early discontinued prior to Week 4 within the period, 28 will be used for the total number of doses planned within the period.
Cumulative orvepitant exposure (mg)	In placebo period, Cumulative dose (in mg) = 0 In orvepitant 10 mg period, Cumulative dose (in mg) = number of doses taken * 10 In orvepitant 30 mg periods, Cumulative dose (in mg) = number of doses taken * 30

Note, if a subject interrupts treatment (for example due to an AE) but subsequently restarts treatment and completes, in total, the planned 4-week treatment period, an adjustment to the actual date range will be applied to the compliance calculation to include only those days that the subject was expected to take treatment (i.e., the dates during which treatment was interrupted will be excluded from the calculation).

Page 38 of 50

NeRRe Therapeutics Ltd Protocol: ORV-PF-01

The following information will be tabulated by treatment:

- Summary of drug duration
- Summary of cumulative orvepitant exposure (in mg)
- Summary of randomised study treatment compliance: Compliance will be summarised quantitatively and qualitatively for the category ( $\leq 50\%$ , >50 to  $\leq 80\%$ , >80 to <100%, =100%, >100 to  $\leq 120\%$ , >120%).

Listings of IMP dispense/administration and drug accountability data will be provided for the Safety Analysis Set.

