8.7.2 Baseline Visit (Visit 2)

A limited set of data will be collected for subjects who withdraw from the study after providing informed consent but prior to randomisation onto the study (Screen Failures).

Eligibility for randomisation will be reviewed based on the results of the eDiary cough score recordings. To be eligible to continue the subject must:

- Have completed the eDiary on at least 4 of the 7 days prior to the Visit
- Meet the cough scale score eligibility criteria (Sections 7.1 and 7.2).

The subject's general health status should be reviewed to confirm that there have been no changes which might make them ineligible.

The Baseline visit will be Day 0. Prior to randomisation on Day 0, the following assessments will be completed:

- Symptom directed physical examination
- Vital signs (after resting for ≥ 5 mins)
- Spirometry

-

Protocol No.: ORV-PF-01 Final V4.0 (US) Page 35 of 85

⁹ Subjects who are unable to complete the DLCO assessment for reasons such as coughing may have this criterion waived

- 12-lead ECG
- Safety labs: blood samples for clinical chemistry and hematology and urine sample for urinalysis
- Blood sample for biomarkers
- Subjects will be asked to complete the study questionnaires: GRS, LCQ, K-BILD, PROMIS SD SF8b, HADS and HARQ
- Subjects will be fitted with an ambulatory cough monitor (ACM), which will be initiated prior to the subject leaving the clinic to monitor cough frequency over the next 24 hours. Immediately after the end of this period the subjects will either return the ACM to the clinic or collection of the ACM from the subjects will be organised.
- A review of changes in concomitant medications and any changes in health status (AEs)

The subjects will be reminded of the eDiary completion requirements and will undergo re-training on the use of the diary if required.

Eligible subjects will be randomised on Day 0 in a 1:1 ratio to either Cohort 1 or Cohort 2, and then within each cohort will be further randomised in a 1:1 ratio to receive either placebo or orvepitant in Treatment Period A. Randomisation will be performed centrally via an IWRS.

Subjects will be dispensed sufficient study medication for 28 days (plus overage) which they should begin taking the evening of the following day before retiring to bed. Starting study medication, the following day enables ACM monitoring to be completed before study medication starts.

8.7.3 Visits 3 and 6

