Visits 3 and 6 should be scheduled 14 (\pm 3) days after the start of each Treatment Period. The assessments are to be undertaken remotely by telephone or videoconference.

A review for adverse events or changes in concomitant medications will be undertaken.

Subjects will complete the GRS and GRC assessments (verbally) and will be reminded of the eDiary completion requirements, as necessary.

8.7.4 Visit 4

Visits 4 should be scheduled 28 (± 3) days after the Baseline visit. The following assessments and procedures will be undertaken at the clinic site or during a home visit:

- Vital signs
- Spirometry
- 12-lead ECG
- Safety labs: blood samples for clinical chemistry and hematology and urine sample for urinalysis
- Blood sample for biomarkers
- Blood sample for orvepitant concentration
- Subjects will be asked to complete the study questionnaires: GRS and GRC, LCQ, K-BILD, PROMIS SD SF8b, HADS and HARQ
- Subjects will be fitted with an ambulatory cough monitor (ACM), which will be initiated prior to the subject leaving the clinic to monitor cough frequency over the next 24 hours.

Protocol No.: ORV-PF-01 Final V4.0 (US) Page 36 of 85

Immediately after the end of this period the subjects will either return the ACM to the clinic or arrangements will be made to collect it from the subject.

• A review of changes in concomitant medications and any changes in health status (AEs)

The subjects will undergo re-training on the use of the diary, if required, and will be reminded of the need to continue to record their IPF Coughing Severity Scale, additional cough scales and other symptom scales in the eDiary during the wash-out period.

Study medication compliance for Treatment Period A will be checked during the visit. The medication bottle will be returned to the patient so that they can take the last dose the same evening, with the medication being finally returned to the site at the same time and using the same method (delivery by patient or collection by courier/ site staff) as the ACM. Compliance will be checked again when the bottle is returned.

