# 5.2 KEY DEFINITIONS

### 5.2.1 Study Day

Study Day 0 is the randomisation day. Subsequent days are numbered consecutively (Day 1, Day 2, etc.). Before Day 0, study days are numbered sequentially with negative values (i.e., Day -1, Day -2, etc.). This notation is used because the first dose of study medication is taken the day after the randomisation visit in Treatment Period A (and the day after Visit 5 in period B).

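### Read literally, SAP Table 2 counts tablets before the last evening's dose but plans for that dose, so a perfectly compliant subject still dosing at Week 4 scores about 96%, not 100%

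*SAP*

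**What the plan says.** SAP 8.7, Table 2, defines compliance as 100 times doses taken over doses planned.

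- **Doses taken** come from the eCRF Drug Accountability and Drug Dispensing pages: tablets dispensed at Visit 2 or 5 minus the "number of tablets remaining in the bottle (at Visit 4 [Period A] or Visit 7 [Period B"]). On supply, Table 2 says "Each bottle contains 34 tablets which is sufficient for the full 28 day dosing period plus overage".
- **Doses planned**: "The total number of doses planned to be taken is the number of days between the first visit in the period" and the Week 4 visit. For a subject who discontinues before Week 4, "28 will be used for the total number of doses planned within the period".
- **Cumulative exposure** is doses taken times 10 or 30 mg in an active period, and 0 in a placebo period.
- **Duration of dosing** is last dose date minus first dose date plus 1.
- **Reporting** uses compliance categories in which exactly 100% stands alone, directly above >80 to <100%.

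The dosing schedule is stated elsewhere. SAP 5.2.1 says that "the first dose of study medication is taken the day after the randomisation visit in Treatment Period A", and likewise the day after Visit 5 in Period B. At the Baseline visit (Protocol 8.7.2) subjects receive medication which "they should begin taking the evening of the following day before retiring to bed". At Visit 4 (Protocol 8.7.4) compliance is checked, and then "The medication bottle will be returned to the patient so that they can take the last dose the same evening"; Protocol 8.7.7 gives the same instruction for Visit 7. Both sections require a second compliance check when the bottle finally comes back. Table 2 does not mention that second check.

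**The concern.** The numerator and denominator appear to cover different days. A bottle counted at the Week 4 visit still holds that evening's tablet, while the number of days between the two visits equals the number of evening doses up to and including that evening.

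What is at stake is how the compliance and exposure tables read. If the visit-day count is used, the =100% row no longer identifies fully compliant subjects. They are pooled with subjects who missed doses, and a subject reaches exactly 100% only if one more tablet than scheduled is gone by the visit. Cumulative milligrams in active periods are low by one dose.

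**Working it through.** **Inputs**

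- Tablets dispensed per period: 34 (SAP Table 2).
- First dose: evening of Day 1, counting Visit 2 or Visit 5 as Day 0 (SAP 5.2.1; Protocol 8.7.2, 8.7.6).
- Last dose: evening of the Week 4 visit, Day *d* (Protocol 8.7.4, 8.7.7 and the schedule of events footnote).
- Target *d* = 28, protocol window 25 to 31; SAP 5.3.2 accepts visits from Day 21 to Day 34.

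**Step 1. Reproduce the plan's own figures.** One tablet per evening from Day 1 to Day 28 is 28 doses, matching the 28-day dosing period. Thirty-four tablets starting on Day 1 last to Day 1 + 34 − 1 = 34, matching footnote b of the SAP 5.3.2 window table. The dose count therefore agrees with the SAP's.

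**Step 2. Apply Table 2 literally to a subject who misses nothing.** Before the visit-evening dose, *d* − 1 doses have been taken and 34 − (*d* − 1) tablets remain. Planned doses are *d*. Compliance = 100 × (*d* − 1)/*d*.

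| Week 4 visit day | Tablets left at visit | Doses counted | Planned | Compliance |
|---|---|---|---|---|
| 21 | 14 | 20 | 21 | 95.2% |
| 25 | 10 | 24 | 25 | 96.0% |
| 28 | 7 | 27 | 28 | 96.4% |
| 31 | 4 | 30 | 31 | 96.8% |
| 34 | 1 | 33 | 34 | 97.1% |

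The shortfall is one dose on every visit day, so the subject always falls in >80 to <100%.

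**Step 3. Apply the final-return count.** On Day 28, 34 − 28 = 6 tablets remain, so 28/28 = 100%. A subject who missed one dose scores 27/28 = 96.4%. That is the score the visit-day count gives a subject who missed none.

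**Step 4. Cumulative exposure on a Day 28 visit.** 10 mg: 27 × 10 = 270 against 28 × 10 = 280 mg. 30 mg: 27 × 30 = 810 against 28 × 30 = 840 mg. Both are short by 1/28 = 3.6%.

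**Step 5. Check against the same table.** Duration of dosing for this subject is 28 − 1 + 1 = 28 days. Table 2 would report 28 days of once-daily dosing, 27 doses and 96.4% compliance for someone who missed nothing.

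**The case against.** The strongest reply is that the visit named in Table 2 may be only an eCRF label. The schedule of events lists study drug collection under Visits 4 and 7, although the bottle is finally collected after the visit-evening dose. If the Drug Accountability page files the final-return count under those visits, the result is 28/28 = 100% and only the wording is loose. The denominator fits this reading, because it allows for the visit-evening dose, and SAP 5.3.2 starts the wash-out on Day 29. This stands as a possibility. The documents do not say which count the page holds, the protocol takes two, and Table 2 names the visit one. Protocol 11.6 gives the SAP precedence on analysis text, so a programmer following it would use the visit-day count.

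A second reply is that the "number of days between the first visit in the period (Visit 2 or 5") and the Week 4 visit could exclude both visit days, giving 27/27 = 100%. The fixed 28 for early discontinuers argues against that, and cumulative milligrams would still be one dose short.

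A reader might also infer that every compliance and exposure figure is biased by one dose. The documents do not support that. Placebo-period exposure is 0 by definition. Duration of dosing uses dates, not tablets. Subjects who stopped before Week 4 have no visit-evening dose to omit. Nor is the denominator always 28: for subjects who reach Week 4 it is the actual visit interval. And a score of 100% need not mean overdosing; a lost tablet or a start one evening early has the same effect.

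**Conclusion.** As written, the rule gives a wrong figure for subjects still dosing at Week 4. A perfectly compliant subject scores 96.4% at Day 28, 96.0% to 96.8% within the protocol window and 95.2% to 97.1% across the SAP's wider limits. Cumulative exposure in an active period is one dose low. This rests on two assumptions: that the count used is the one made at the visit, which is what Table 2 names, and that the interval between visits is counted as 28 for a Day 28 visit.

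The consequence is small. Compliance and exposure are summarised descriptively. The per-protocol set (SAP 4.3 and 4.4) has no numeric compliance threshold, and the primary analysis on the full analysis set does not use compliance. A reader might infer that the efficacy conclusions or the analysis sets are at risk; nothing in the documents supports that. The point is a low-priority correction worth making because it is cheap and because the =100% row would otherwise mislead.

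**What to change.** In SAP Table 2, take tablets remaining from the count made when the bottle is finally returned after the last dose, which is the second check required by Protocol 8.7.4 and 8.7.7. Keep the current denominator. Before finalising the text, confirm that this count is recorded on the eCRF Drug Accountability page; the protocol requires the check but does not say where it is entered.

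If only the visit-day count exists, add the visit-evening dose to doses taken when it is documented as taken. That corrects both compliance and cumulative milligrams. Reducing the denominator by 1 instead would give 27/27 = 100% but leave cumulative exposure at 270 or 810 mg.

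The cost is one sentence in Table 2 and one check of the eCRF. No new procedure is needed, since the protocol already requires the second check.
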